Current Clinical Gaps Identified: Status of CVRS, lipid screening or treatment of dyslipidemia in RA is far from optimal, even in Medicare age group patients. Traditional CVD risks and RA-specific risk/s are well noted be to be associated with greater CVD in RA. However, the presence of RA does not always trigger CVRS or treatment. In RA patients (≥ 65 years), primary lipid screening was performed in 45% (7), an age group where all patients should receive dyslipidemia screening, regardless of their RA status. Adjusted predicted probabilities of lipid screening were 26% for RA patients seeing rheumatologist alone, to 44-48% for patients with some primary care physician visits (7). In another study, one third of RA patients did not have any lipid testing (18- 19). Furthermore, upto 26% of RA patients without CVD have sufficiently high risk for CVD to require statin therapy, yet and most of them remain untreated (20).

Potential reasons for poor CVRS in RA, despite the indication may include lack/limited knowledge among RA patients and their PHCP's about the CVD risk. Lack of knowledge in general about CVD risks in women and their PHCPs has been previously reported. Women do not always perceive themselves to be at risk for CVD (21). Furthermore, existent medical literature is lacking in published studies in the United States in RA that (i) ascertain patient or physician awareness of CVD risks, or (ii) compare the rates of CVRS pre and post EI against RA patients receiving usual care from PHCP. These are lost opportunities to make PHCP's aware of the existent gap in knowledge and thus the need for changing behaviors. In a study done in United Kingdom, only 32% of general practitioners identified RA as a risk for CVD (22). They reported lack of educational resources on this matter. Secondly, lack of clarity on primary responsibility for CVRS in RA, in a patient seeing two or more physicians, may contribute to low CVRS and treatment. RA patients who saw their primary care physician in the past year, in addition to their rheumatologist, were more likely to get CVRS by their PHCP (23). Time constraints during each visit may also burden the PHCP. Performance of CVRS to Physician Quality Reporting Initiative (PQRI) in RA may be helpful.

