We propose a longitudinal of 300 RA (150 with and 150 without EI), to test for (*primary outcome*) change in CVRA at 2-3 months following web-based EI, and compare that with CVRA changes among RA patients without IE. The proposed secondary outcomes will explore the rates of CVRS via medical chart review among RA patients with and without IE. Consenting participants (RA patients (n=300) and PCHPs) will have (a) baseline survey on CVRA, followed by a short EI delivered via YouTube video (n=150), followed by immediate and 2-3-month follow up surveys, to quantitate changes in CVRA, (b) a medical record review of participating RA patients (n=300) will be undertaken (records from preceding one year duration) and at 12 months (after baseline visit) to determine the changes in CVRA evaluations and the EI. Care will be taken to avoid enrollment of PCHPs providing care to RA patients not in the EI arm, to not confound the results.

Educational approach is discussed in the section I. We expect to reach out to 600 RA patients at RUMC and JSH, with the goal of recruiting 300 RA patients over 12 months. This screening-to-enrolment ratio is consistent with previously observed 10:9 ratio for survey-based one-visit

studies at RUPC and JSH. We expect to reach our expected goal of 300 RA patients even if screening-to-enrollment ratio erodes to 10:5. Sample size calculation: To show an improvement of 20% in overall CVRA, with 90% power and 0.05% alpha error, we need 127 RA patients in each group.

H. Innovation: We did not find on our review of current medical literature (PubMed and Ovid Medline) using the search terms "Rheumatoid arthritis" and "educational intervention" and "web" for any existent EI studies that study patient-PHCP CVRA or utilize a YouTube based EI to improve CVRA. Furthermore, use of patient-PHCP dyad for CVR EI has not been reported. We feel confident that our study idea is original and has significant advantages over existent methods as it is easier, quicker and has significant potential applications. The you tube video EI if successful can be offered through National organizations e.g. American College of Rheumatology or Arthritis Foundation; and can be made available to large numbers of RA patients worldwide with less resources utilization and advantages of privacy, flexibility and access to users.

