meeting the following criteria (i) Diagnosed with RA with following criteria: Inflammatory symmetric polyarthritis of \geq 6 weeks, with physician documented synovitis in medical records (past or current) consistent with RA, with or without rheumatoid factor, anti cyclic citrullinated peptide or radiologic evidence of RA. Exclusion of another etiology for above. (ii) Receipt of care by rheumatologist at either RUMC or JSH. This will allow us access to full medical records to correctly gauge the prevalence of CVRS. (iii) Informed consent. *B. PHCP*: (i) Physicians providing primary care to the RA patients recruited for this study for the El group. Definition of PHCP has been previously provided (section F), (ii) Informed consent (iii) Not providing PHCP to RA patients in the non-El group.

1.2. *Methods: 1.* Education intervention development phase: The primary outcome of the intervention development phase will be patient-centered EI video and PHCP-centered education EI to increase CVRA in RA. The interdisciplinary study team will develop a multi-level web-based EI for CVRA targeted to RA patients and their PHCPs. This team will consist of 3-6 RA patients and the panel of experts in rheumatology, preventive cardiology/endocrinology, and experimental health and social psychology. To improve overall RA patient outcomes, our educational approach for the web-based EI is specifically aimed at changing the knowledge, and thus health behaviors of RA patients and their PHCP.

Educational Approach: In the **development of the web-based EI** (Table 1, Figure 1), we will utilize credible, useful, innovative educational platform and input from opinion leaders in the therapeutic areas. All educational content will be learner centric in approach, language and content (Table 2). Content appropriateness of the tailored intervention will be verified by the health experts. Processes of change will be focused on increasing RA patients or their PHCP CVRA in general and in RA, and increasing their awareness of the need for change. This 20-30 minute You Tube EI video will be developed using scientifically researched content (Table 2).

	Table 2: Develo	opment of Content for Educational web-based Intervention
Audience	Major Areas in Content Develo	Key Features
Patients	1) What is CVD and CVD in USA	Definition of CVD, Leading cause of death
	2) CVD in Women	Leading cause of death in women

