Perception of risk of heart disease scale (PRHDS) (8), Heart Disease Fact Questionnaire (HDFQ)(24) will be modified to include some items on autoimmune diseases (including RA).Relevant components of the Behavioral Risk Factor Surveillance System (BRFSS) 2013 survey from US Centers for Disease Control 2013 (22), This will include sections and modules on hypertension awareness (2 items), cholesterol awareness (3 items), chronic health conditions (12 items), tobacco use (5 items), pre diabetes and diabetes (10 items), cardiovascular health (7 items), Mental Illness and Stigma (10 items) and Emotional Support and life satisfaction (2 items).

2. The content of PHCP surveys: A survey to assess CVRA in PHCPs will be developed. This survey development will be guided by the co-investigators and a questionnaire adapted from BRFSS and National Health and Nutrition Examination Survey (21) that was used previously in a similar study (8). The survey will be modified to include questions about CVRA in women and in autoimmune diseases. In addition, five hypothetical case scenarios will be created with various combinations of CVR in patients with and without autoimmune disease, and PHCP will be asked to select the CVRS indicated and strategies to optimize the patient's individual CVD risks.

The finalized surveys used for CVRA will be pretested among 5-10 RA patients and Physicians.

I.4. Incentives: For the participating RA, a \$50 honorarium will be provided at baseline and follow up visit (Table 4).

I.6. Data: *Patient*: Demographic (age, gender, ethnicity), Socio-economic status (education) and RA pertinent data (duration, presence of Rheumatoid factor and/or anti cyclic citrullinated peptide, bony erosions, medications (including steroids and biologics)). Self reported CVRA (Overall, Traditional and RA) will be assessed at baseline, immediately after viewing the video (follow up 1), and after 2-3 months (follow up 2).

PHCP: Demographic (age, gender, ethnicity), type of physicians (Internal Medicine, Family practice, Rheumatologist), years since completion of residency in Internal Medicine or Family Practice, years since board certification, currently board certification status, setting of practice (academic, community or private practice), rank (if any), approximate number of RA patients seen yearly. Self reported CVRA (Overall, Traditional and RA) will be assessed at baseline, immediately after viewing the video (follow up 1), and after 2-3 months (follow up 2).

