For patients (a) Overall CVRA (ORA), (b) Traditional CVR awareness (TRA) (c) RA CVR awareness (RARA) will be calculated. Awareness of all 18 CVR being tested (listed in section 1) will denote 100% CVR awareness. To score ORA, patient's correct responses denoting awareness to each of the 18 CVR being tested will be calculated in percentage of total responses. Domain-specific CVR awareness for traditional CVR (TRA) and RA (RARA) will be scored separately using the same strategy.

CALL AND AND A

Paired t tests to compare pre and post (Follow up 2) patient overall CVRA for our primary outcome of interest will be performed. Effect size of gains in overall CVRA for RA patients after EI (Follow up survey 2 and baseline) will be calculated. We will then compare percent change in overall CVRA rates (between baseline and follow up 2) using chi square analysis, among EI and non-EI patients with RA. A p value of ≤ 0.05 will be considered significant on two tailed tests.

Aim 2B. To explore changes in cardiovascular risk screening (CVRS) at the primary health care visits among RA patients with and without EL.

The medical records of RA patients with and without EI will be reviewed in electronic medical record, and analyzed using standardized checklist to assess the prevalence of CVRS and CVD risk reduction plan (meaningful use). Changes in CVRS rates among EI and non EI groups will be calculated, and compared using chi square analysis. A p-value of ≤ 0.05 will be considered significant on two tailed tests.

Exploratory analysis on improvement in PHCP overall CVRA using analysis similar to those discussed for aim 2a will be undertaken, a post hoc power analysis and effect size will be obtained. In addition exploratory univariate and multivariate logistic or linear regression analysis for patient and PHCP correlates of CVRS (baseline) and change in CVRS will be performed. Improvements in Traditional and RA-specific CVRA among RA and PHCPs will be assessed.

J. Dissemination plan: The first step in disseminating outcomes will be to share the results of the study with the participants of the study, RA patients and their PHCP.

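### Provider type and primary care visits are not listed as patient-level data for both groups, so Aim 2B has no listed variable to adjust for them and survey-based PHCP correlates cover the EI group only

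*Protocol*

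**What the plan says.** **Who supplies PHCP data.** Under the inclusion criteria in Protocol section I.1, eligible PHCPs are "Physicians providing primary care to the RA patients recruited for this study", which the same sentence limits to the EI group. A further criterion is "Not providing PHCP to RA patients in the" non-EI group. Table 4 plans 50 PHCPs.

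**What is listed.** Section I.6 puts "type of physicians (Internal Medicine, Family practice, Rheumatologist", years since training, board status, practice setting and PHCP awareness under PHCP data. Its patient list covers demographics, education, RA data and patient awareness. The CVRS checklist in I.1 has no item for provider type or for whether a primary care visit took place.

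**Why this could matter for screening.** Section E reports: "Adjusted predicted probabilities of lipid screening were 26% for RA patients seeing rheumatologist alone, to 44-48% for patients with some primary care physician visits". It adds that RA patients who saw a primary care physician as well as a rheumatologist in the past year were more likely to be screened by their PHCP. Section F lets the patient name a rheumatologist, family practitioner, internist, other specialist or mid-level provider as PHCP.

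**What is analysed.** The design is "300 RA (150 with and 150 without EI"), and no random allocation is described. In section I.7, Aim 2B compares changes in CVRS rates between groups by chi-square. The same section says regressions for "patient and PHCP correlates of CVRS (baseline) and change in CVRS will be performed".

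**What is within reach.** Section G.1 states that "a medical record review of participating RA patients (n=300) will be undertaken". Table 5 makes identifying the PHCP a task of both the baseline and the one-year chart review, with no limit to the EI group.

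**The concern.** The protocol cites a determinant of its own secondary outcome, then does not list it among the data for every patient. Two analyses are affected.

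- **Aim 2B.** The groups are not described as randomised. They may therefore differ in how many patients see only a rheumatologist. Such a difference could imitate or mask an EI effect on screening, and the planned chi-square has no adjustment for it.
- **PHCP correlates of CVRS.** Baseline CVRS is available for all 300 patients and precedes the EI, so provider type and visit pattern could be examined in everyone. If provider data come only from enrolled PHCPs, the analysis is confined to EI patients whose PHCP took part.

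A smaller mismatch adds to this: I.6 names three physician types, while section F also allows other specialists and mid-level providers.

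**Working it through.** The protocol gives no figure for this point. Its one computed figure, 127 per group in G.1, concerns the awareness outcome and has no bearing here. It can be reproduced with an assumed 40% versus 60%, two-sided alpha 0.05 and 90% power: (1.960 + 1.282)² × (0.4×0.6 + 0.6×0.4) / 0.2² = 126.1, rounded up to 127.

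**Step 1: coverage of survey-derived PHCP items.** Inputs: 150 EI and 150 non-EI patients (G.1); PHCPs enrolled for EI patients only (I.1).
- Patients who can carry these items: at most 150 of 300 = 50%.
- The share is lower if an EI patient's PHCP declines or is barred for also treating non-EI patients.

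**Step 2: possible bias in a cross-sectional screening rate.** Inputs: 26% and 44-48% (section E), a gap of 18 to 22 points. The imbalance in rheumatologist-only care is assumed, because the protocol gives none. Formula: spurious difference = imbalance × gap. The last column is the normal-approximation chance of a significant result in that direction with 150 per group, two-sided 0.05 and the two groups' mix centred on 50:50. The nominal value in one direction is 2.5%.

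| Assumed imbalance | Spurious difference (points) | Chance of significance in that direction |
|---|---|---|
| 10 points | 0.10×18 = 1.8 to 0.10×22 = 2.2 | 5-6% |
| 20 points | 0.20×18 = 3.6 to 0.20×22 = 4.4 | 10-12% |
| 30 points | 0.30×18 = 5.4 to 0.30×22 = 6.6 | 16-22% |

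These figures concern lipid screening at one time point. Aim 2B compares changes, so whatever part of the gap is stable over the year cancels. CVRS also has several items besides lipids, and the protocol gives no comparable gap for those.

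**Step 3: what full coverage would buy for baseline correlates.** Power to detect 26% against 44% or 48%, two-sided 0.05, patients treated as independent, split between visit patterns assumed:

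| Split (rheumatologist only : some primary care) | 300 patients | 150 patients |
|---|---|---|
| 50:50 | 0.91 / 0.98 | 0.64 / 0.80 |
| 20:80 | 0.74 / 0.89 | 0.43 / 0.59 |

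Clustering is ignored. With 50 PHCPs for 150 EI patients (150/50 = 3 each on average if all were covered), information on provider characteristics would be somewhat less than these figures suggest.

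**The case against.** Three stronger readings are tempting, and the documents do not support them.

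- **A reader might infer that Aim 2B cannot be adjusted for provider type at all.** It can. The patient names the PHCP (section F), charts are reviewed in both groups (G.1), identifying the PHCP is a chart-review task (Table 5), and outside PHCPs are contacted for records whatever the group (I.2, assessment in patients). The gap is in what is listed, not in what can be obtained.
- **A reader might infer that the protocol's figures tie PHCP type to screening.** The contrast is between visit patterns: "26% for RA patients seeing rheumatologist alone, to 44-48% for patients with some primary care physician visits". A patient who names a rheumatologist as PHCP may still see an internist. The figures bear on PHCP type only indirectly.
- **A reader might infer that the whole PHCP-correlates analysis loses half its patients.** That holds for items only the PHCP survey can supply. Their restriction to the EI group follows from a deliberate rule against contamination. It need not hold for PHCP type.

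It can also be said that I.6 is not exhaustive: the patient survey in I.3 collects history, weight and height that I.6 omits. Abstraction fields and covariates are often settled in data forms or an SAP, and nothing here touches a primary outcome. Part of this stands. Absence from I.6 does not prove that the field will go unrecorded, and the priority is modest. But identifying a provider is a task rather than a recorded variable, and no later analysis plan can adjust for a field that was not abstracted.

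**Conclusion.** The point holds as a gap in the listed data. Two consequences are firm, given the protocol's lists:

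- Aim 2B has no listed variable for adjusting for provider type or visit pattern, in a comparison with no randomisation described.
- Survey-derived PHCP correlates can be estimated in at most 150 of 300 patients, all in the EI group.

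The size of any bias is not established. About 4 points is an illustration that rests on an assumed 20-point imbalance, on the section E lipid figures applying to this population, and on a cross-sectional comparison. The planned comparison of changes would show less, and none if the gap were fully stable. Aim 2B is a secondary outcome worded as exploratory, and the correlates regression is exploratory. The change is worth making because it is cheap and improves both analyses, not because the trial's main conclusion is at risk.

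**What to change.** - **Chart-review form, all 300 patients.** Record any primary care visit in the baseline year (yes/no), PHCP type in the section F categories (including other specialist and mid-level provider), and PHCP setting (RUMC, JSH or outside). List these in I.6 as patient-level data. Keep the visit field to the baseline year: the patient video covers contacting the PHCP, so later visits could themselves result from the EI.
- **Aim 2B in I.7.** Keep the chi-square and supplement it with a regression of one-year CVRS on group, baseline CVRS, primary care visit and PHCP type.
- **Correlates in I.7.** Run the PHCP-type and visit correlates of baseline CVRS on all 300 patients. State that survey-only predictors (PHCP awareness, years since training, board status) are estimable in EI patients only.

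The cost is slight extra abstraction in a review that already has to identify the PHCP, and a few lines in I.6 and I.7. Sample size, visits and the primary outcome do not change.
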